**ABBREVIATIONS AND DEFINITIONS OF TERMS**

| Abbreviation | Definition  |
|---------------------|--|
| CBT                 | Cognitive-Behavioral Therapy                               |
| CSC                 | Coordinated Specialty Care                                 |
| DUP                 | Duration of Untreated Psychosis                            |
| FEP                 | First Episode Psychosis                                    |
| LAR                 | Legally Authorized Representative                          |
| MOS                 | Medical Outcomes Study                                     |
| NC                  | North Carolina   |
| NIMH                | National Institutes of Mental Health                       |
| NSR                 | Non-significant Risk                                       |
| OASIS               | Outreach and Support Intervention Services                 |
| PI                  | Primary Investigator                                       |
| PSS                 | Peer Support Specialist                                    |
| PWS                 | Psychological Wellbeing Survey                             |
| SIAS                | Social Interaction Anxiety Scale                           |
| SSD                 | Schizophrenia Spectrum Disorder                            |
| UCLA                | University of California, Los Angeles                      |
| WAI-I               | Working Alliance Inventory – guided Internet interventions |

**PROTOCOL SYNOPSIS**

|  |   |
|--|---|
| Study Title                               | Horyzons: Implementation in Clinical Practice   |
| Funder                                    | North Carolina Department of Health and Human Services,
University of North Carolina at Chapel Hill  |
| Clinical Phase                            | Phase I   |
| Study Rationale                           | The purpose of the present study is to investigate the feasibility and acceptability of implementing a moderated online social media platform with therapeutic content, Horyzons, as a part of care received at first-episode psychosis (FEP) clinics across North Carolina.  |
| Study Objective(s)                        | 
Examine the feasibility and acceptability of implementing Horyzons at NC FEP clinics through the following objectives:
 
 
1. Assess change in psychological measures across the three-month (cohort 1) and six-month (cohort 2) study period (primary)
 
2. Ability to meet our recruitment targets
 
3. Evaluation of the safety and privacy protocol
 
4. Evaluate frequency and types of engagement on Horyzons
 
5. Identify barriers/facilitators to implementing Horyzons
 
 |
| Test Article(s)
(If Applicable)       | Horyzons is a private digital platform that includes curated therapeutic content surrounding issues such as generalized anxiety, social anxiety, social functioning, depression, and distress tolerance. The site also includes a social media function, in which participants and peer support specialists (PSS) can post text, images, and videos. The site is moderated by graduate students and trained clinicians.   |
| Study Design                              | This is an open trial enrolling both clients from NC FEP clinics. FEP clients will participate in the experimental arm of the trial (access to Horyzons), and FEP clinicians will not. We will also ask clients and clinicians to complete qualitative feedback about Horyzons.   |
| Subject Population                        | Inclusion Criteria   |
| key criteria for Inclusion and Exclusion: | 
 
1. Clients must be between the ages of 16 and 35
 
2. Clients must have a diagnosis of schizophrenia, schizoaffective disorder, schizophreniform disorder, or Unspecified Schizophrenia Spectrum or Other Psychotic disorder
 
   |

3. Clients must be receiving services at one of the four FEP clinics in North Carolina (OASIS, Encompass, Eagle, or SHORE) or one of the three UNC STEP-affiliated clinics (Carr Mill Mall, Vilcom Center, Main Wake Clinic)
4. Clients must not have had thoughts of harming themselves in the month before enrollment
5. Clients must not have been hospitalized for psychiatric reasons in the three months before enrollment
6. Clients must not have had a psychiatric medication change in the month before enrollment
7. Clients must have access to the internet through a phone, tablet, or computer

**Exclusion Criteria**

1. Clients who do not speak English will not be considered for enrollment
2. Adult clients (18+ years old) with legal guardians (LARs) will not be considered for the study

|                           |   |
|---------------------------|---|
| Number Of Subjects | Cohort 1: 25 client participants with SSDs, 12 clinician participants from NC FEP clinics; Cohort 2: 37 client participants with SSDs, 11 clinician participants from NC FEP clinics.   |
| Study Duration     | For Cohort 1, each subject's participation will last 3 months from baseline to post-treatment; the entire study for this group is expected to last approximately 3-4 months. For Cohort 2, each subject's participation will last 6 months from baseline to post-treatment; the entire study for this group is expected to last approximately 6-7 months.   |
| Study Phases       | Screening - Completed prior to the first virtual appointment via a telephone screen to confirm study eligibility.  |
| Screening          |   |
| Study Treatment    | Baseline - Participants in both cohorts who are deemed eligible schedule a virtual appointment with the study coordinator to obtain consent, HIPAA authorization, and complete the baseline assessments (Demographics, UCLA Loneliness Scale, MOS Social Support Survey, SIAS, short-form PWS). Client participants are then oriented to the Horyzons site. Participants in the second cohort only also complete other assessments (Questionnaire about the Process of Recovery, Social Anxiety Scale for Social Media Users, Modified Colorado Symptom Index, and Twente Engagement with eHealth Technologies Scale). |
| Focus Groups       | Study Treatment - Client participants will be given access to the digital platform Horyzons for three months. Weekly engagement is decided by the participant. Digital access is available daily, digital  |

access to PSS and online therapists is made available daily, and virtual “Horyzons Hangs” are hosted over Zoom by PSS biweekly.

Mid-treatment- Participants in both cohorts will complete assessments (UCLA Loneliness Scale, MOS Social Support Survey, SIAS, short-form PWS, WAI-I, and Perceived Autonomy Support Scale). Participants in the second cohort only also complete other assessments (Questionnaire about the Process of Recovery, Social Anxiety Scale for Social Media Users, Modified Colorado Symptom Index, and Twente Engagement with eHealth Technologies Scale).

Post-treatment – Participants in both cohorts will complete assessments (UCLA Loneliness Scale, MOS Social Support Survey, SIAS, short-form PWS, WAI-I, and Perceived Autonomy Support Scale). Participants in the second cohort only also complete other assessments (Questionnaire about the Process of Recovery, Social Anxiety Scale for Social Media Users, Modified Colorado Symptom Index, and Twente Engagement with eHealth Technologies Scale). An additional feedback survey and qualitative interview are completed.

Additional assessment timepoints for the second cohort: Participants in the second cohort will complete the following assessments at 1.5 months and 4.5 months following baseline (WAI-I, Perceived Autonomy Support Scale, Twente Engagement with eHealth Technologies Scale).

Focus Groups- Participating clinicians and PSS take part in small focus groups to discuss feasibility, acceptability, and implementation of Horyzons at their NC FEP clinics.

---

#### **Efficacy Evaluations**

Primary outcomes (both cohorts) - The UCLA Loneliness Scale and MOS Social Support Survey (total score) will be used to assess subjective feelings of loneliness and social support.

Secondary outcomes (both cohorts) - The SIAS and short-form PWS will be used to assess subjective feelings of social anxiety and psychological wellbeing.

Tertiary/Exploratory Outcomes (both cohorts) - Quantitative and qualitative feedback collected at post-treatment and in focus groups will be used to explore feasibility and acceptability of Horyzons as a support tool in NC FEP clinics. Subscales from the MOS Social Support Survey and the short-form PWS as well as total scores from the WAI-I and Perceived Autonomy Support Scale may be explored in data analysis. Among the second cohort only, other scales/subscales such as the Questionnaire about the Process of Recovery, Social Anxiety Scale for Social Media Users, Modified

---

|  |   |
|--|---|
|  | Colorado Symptom Index, and Twente Engagement with eHealth Technologies Scale may be explored in data analysis.   |
| Safety Evaluations              | A safety plan for Horyzons was developed before participants joined the Horyzons digital platform by PI [name] and study coordinator [name]. All safety measures were approved by the director of each NC FEP clinic.   |
| Statistical And Analytic Plan   | Analyses will primarily be descriptive in nature. We will calculate means, standard deviations, and effect sizes of the primary outcomes (loneliness, social support) and secondary outcomes (social anxiety, psychological wellbeing).   |
| DATA AND SAFETY MONITORING PLAN | Privacy and online safety will be managed in accordance with the 'Online social networking' guidelines published by 'Cybersmart', a national cybersafety and cybersecurity education program managed by the Australian Communications and Media Authority (ACMA). Online safety will be monitored by Horyzons moderators (clinicians involved in the project, peer support specialists, graduate students in the Department of Psychology and Neuroscience) with supervision from the Principal Investigator. [name] will function as the Project Medical Officer. |

## **1 BACKGROUND AND RATIONALE**

Schizophrenia is one of the most devastating and costly of the medical/psychiatric disorders. In the last 25 years, first episode psychosis (FEP) services have emerged to thwart the high relapse rates associated with this disorder and increase client treatment engagement. Increasing evidence shows that such services lead to improvements in symptoms, social functioning, quality of life and treatment satisfaction (1). In the United States, these services have come to be known as Coordinated Specialty Care (CSC).

There are a number of North Carolina based CSC programs that provide early psychosis treatment to adolescents and young adults who have recently experienced the onset of psychosis. Specifically, there are 4 CSC programs in operation in North Carolina, including the Outreach and Support Intervention Services (OASIS) clinic in Chapel Hill, the Eagle Program for First Episode Psychosis in Charlotte, the Wake Encompass Program in Raleigh, as well as the SHORE program in Wilmington. Each CSC clinic employs a multidisciplinary team of providers that promotes recovery, person-centered and culturally competent evidence-based interventions with the goal of decreasing illness severity and reducing or preventing disability by intervening early in the course of illness. The goal of these programs is to help individuals get back "on track" in order to achieve school, work, relationship and other life goals. Evidence-based services including CBT-based individual psychotherapy, evidence-based pharmacology, supports for wellness and primary health coordination, family education and support, case management, supported employment and education, and/or peer support with an emphasis on shared decision-making, values, and recovery.

Young people receiving services from CSC programs typically attain significant positive outcomes including decreased rates of hospitalization and improved social and occupational functioning within an average of two years of treatment (2). However, treatment benefits are usually not maintained over time (3-4) in particular when clients are less engaged in treatment or have recently experienced discharge from the program. For instance, the benefits of early intervention seen at the end of 2 years may not persist at 5 years (5). There is a need, therefore, to explore ways to provide ongoing support for individuals experiencing first episode psychosis. This support should address specially what some have called "social network crisis" experienced by the FEP population. This refers to the limited social networks and community support that individuals with psychosis generally have. Innovative approaches through internet-based interventions may shed valuable light on the issue of maintaining treatment effects derived from FEP services, and offer additional social support to those enrolled in such services.

Additionally, the proposed research is aligned with the NIMH strategic objective of striving for prevention and cures through the study of mechanisms of therapeutic action. Specifically, it aligns with the goals of developing new treatments based on discoveries in the behavioral sciences and testing interventions for effectiveness in community practice settings. This project in essence builds and extends the findings of research on the effectiveness of CSC and looks to determine whether these benefits can be extended beyond CSC in a web-based platform delivered to individuals in the community.

We suggest that internet-based interventions have the potential to provide cost-effective, non-stigmatizing, constantly available support to FEP people. These interventions, especially those aimed to strengthen social networks, can be used to counteract social isolation and disadvantage; increase functional outcomes and engagements (6); reduce symptomatology; and improve uptake and acquisition of therapeutic strategies.

These also provide an entirely new approach in which participants can safely self-disclosure, take positive interpersonal risks, gain perspective, broaden and rehearse coping skills, obtain encouragement and validation, and learn how to solve problems (7).

The purpose of this study is to examine the feasibility and acceptability of implementing Horyzons across two cohorts of clients receiving routine care at clinics across North Carolina that provide services to individuals experiencing schizophrenia spectrum and other unspecified psychotic disorders, including those in their first episode of psychosis (FEP). Horyzons is an online platform that integrates: i) peer-to-peer on-line social networking; ii) individually tailored interactive psychosocial interventions; and (iii) trained moderation. First tested in Australia, this type of intervention has not been evaluated as part of standard service provision to individuals with psychosis in the US.

Of note, the pilot study that was completed at the Outreach and Support Intervention Services (OASIS) clinic incorporated Horyzons as an adjunct to care rather than part of routine services. Also, there will be no incentives provided for engagement in Horyzons during the proposed implementation as our goal is to see examine the process by which clients are referred and maintained in the program. As such, we seek to evaluate the extent to which Horyzons can be integrated into typical treatment at four FEP clinics across North Carolina.

## **2 RESEARCH DESIGN AND METHODS**

### **2.1 OVERVIEW**

Participants (clients) will be given access to Horyzons (which is considered a “non significant risk” medical device and is described below) from their date of enrollment up to 3 months in the first cohort (enrolling January 2021) and up to 6 months in the second cohort (enrolling February 2022). Horyzons will be monitored daily (two hours per weekday & one hour per weekend day) by trained peer support specialists, master's level clinicians, [name] (PI), and/or graduate students in the Department of Psychology and Neuroscience at UNC. In an effort to facilitate and monitor engagement, a protocol is in place that directs moderators to contact participants via text message and/or email if an he/she/they have not logged onto the platform for two weeks, and via telephone if a participant remains inactive for an additional two weeks. The principal investigator, [name], will lead weekly supervision calls to ensure appropriate care and support of clients involved in this project, to discuss case conceptualization and suggestions for engaging clients in the platform, as well as to monitor any potential safety concerns.

Overview of Horyzons. Horyzons is an online social media platform that integrates: i) peer-to-peer on-line social networking; ii) individually tailored interactive psychosocial interventions; and (iii) expert moderation.

*Peer-to-peer online social networking (the “Community”).* The ‘community’ page includes a web feed where clients and moderators can post comments, information, upload pictures and videos, and ‘like’ different content. Moreover, the system includes a ‘wall’ function displaying the activity of individual users, and a ‘network’ (similar to a ‘friends’ function). The open trial also incorporates the participation of peer support specialists. Peer supports are individuals with lived experience of severe mental illness who are familiar with the Horyzons platform and affiliated with one of the first episode clinics in North Carolina

at which this study will be implemented. These individuals are part of the investigational staff who will be interacting with participants for research purposes, and will also provide feedback (via focus groups with clinicians) upon completion of the study. Their primary function will be to induct clients to the platform, reach out to inactive participants, answer any questions clients may have about the site, and help facilitate discussion in the cafe and other sharing areas of the platform. Research staff at the university and/or clinicians at the FEP clinics in North Carolina will train and supervise all Horyzons peer support specialists, and will also be asked to provide feedback through participation in focus groups.

*Interactive psychosocial interventions.* Horyzons includes a range of tailored interactive psychoeducation pathways divided into separate steps. These pathways target key risk factors and salient domains in the early recovery process including: (a) managing symptoms of (social) anxiety, (b) developing strategies to cope with depressive symptoms, and (c) improve social skills and functioning. Individuals are able to select which pathways they would like to utilize based on their treatment goals. All pathways are available to all participants in this study.

*Expert Moderation.* Peer support specialists, clinicians with significant experience in the psychosocial treatment of FEP clients, as well as graduate students with relevant clinical/research experience with individuals with psychosis will serve as expert moderators. Their role is to provide guidance, monitor participants' clinical status and ensure the safety of the social networking environment. The moderator reviews interactivity in the social networking space and information from individual participants' modules to monitor clinical risk. The Horyzons Moderation Checklist will be completed by each moderator every time he/she moderates the platform. The checklist is designed to ensure moderators complete the appropriate safety checks during the moderation session, and to give moderators ideas as to how to engage users.

Treatment period. Participants in both cohorts will complete study assessments at baseline, mid-treatment, and post-treatment. Participants in the second cohort will complete two additional assessments before and after mid-treatment assessment at 1.5 months and 4.5 months following baseline, respectively.

For all administration of assessments/interviews, the study coordinator will use screen sharing via secure videoconferencing to complete measures with the participant. Baseline assessment will be completed alongside the review and completion of informed consent and onboarding of participants onto the Horyzons platform. Participants will complete a mid-treatment assessment with the study coordinator or other trained research assistant, which corresponds to approximately 6-8 weeks after onboarding in the first cohort and approximately 12 weeks after onboarding in the second cohort. Participants will also meet with the study coordinator or other trained research assistant for a post-treatment assessment after clients have engaged with the platform for 12 weeks in the first cohort and 26 weeks in the second cohort. At post-treatment, both clients and clinicians (procedures described below) will be provided with an optional feedback form as a way of better understanding their experience with the platform and collecting suggestions for improving the site. Individual feedback interviews with clients will also be completed at post-treatment, lasting 60 minutes. These interviews will address participants' social relationships, experiences with loneliness, and thoughts about connecting with others through Horyzons.

In order to evaluate the extent to which engagement in Horyzons may have impacted participants' perceptions of their social environment, participants will be asked to complete brief psychological measures. In the first cohort at baseline, mid-treatment (6-8 weeks), and post-treatment (12 weeks), participants will complete measures of loneliness (UCLA Loneliness Scale), social support (MOS Social Support Survey), social anxiety (Social Interaction Anxiety Scale), recovery (short form PWS - Psychological Wellbeing Scale), and therapeutic alliance (WAI-I and Perceived Autonomy Support Scale).

The second cohort will complete all aforementioned measures at baseline, mid-treatment (12 weeks), and post-treatment (26 weeks) alongside additional measures of personal recovery (Questionnaire about the Process of Recovery), social anxiety related to use of social media (Social Anxiety Scale for Social Media Users), and self-report psychological symptomatology (Modified Colorado Symptom Index). A self-report measure of engagement (Twente Engagement with Ehealth Technologies Scale) will be completed at baseline, mid-treatment, and post-treatment as well as at two additional timepoints: 1.5 months and 4.5 months following baseline. Measures of therapeutic alliance (WAI-I and Perceived Autonomy Support Scale) will be administered at 1.5 months, mid-treatment, 4.5 months, and post-treatment only. As this platform will be provided as part of clients' routine clinical care, we will also share clinical impressions and other relevant clinical information to the clinical team at the client's respective FEP clinic.

Feedback from providers or staff (i.e., program directors, clinicians, peer specialists) will be collected through focus groups (lasting 60-75 minutes). Prior to initiating the focus groups, providers will complete a brief survey which will include (a) general feedback questionnaire about Horyzons and (b) service mapping questions; regarding the latter, program directors and clinicians/peer specialists will complete separate service mapping questionnaire specific their roles. In the qualitative focus groups, all providers will be asked to provide feedback about their perceptions of their clients' experiences using the platform, and will also be asked to provide opinions about facilitators/barriers to engagement and challenges to implementing and disseminating the Horyzons platform within the clinic. All individual interviews and focus group feedback sessions will be conducted virtually via secure videoconferencing and will be led by the Horyzons study coordinator and/or a graduate student in clinical psychology at UNC-Chapel Hill. All feedback sessions will be digitally recorded, and will be de-identified and transcribed by a member of the research team or by a transcription service. The purpose of these recordings and transcriptions is to allow the research team to examine the feedback provided in the focus groups for the purposes of improving the process of integrating this type of treatment in clinics that provide mental health care to individuals with first episode psychosis.

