#### **4.2.2 POST-TREATMENT PROCEDURES**

The study coordinator will meet virtually with client participants for approximately 1-1.5 hours to complete the post-treatment measures. Client participants will complete virtual copies of the UCLA Loneliness Scale, MOS Social Support Survey, SIAS, short form PWS, WAI-I, and Perceived Autonomy Support Scale. Participants in the second cohort only will complete additional measures at post-treatment (e.g., Questionnaire about the Process of Recovery, Modified Colorado Symptom Index, Social Anxiety Scale for Social Media Users, Twente Engagement Questionnaire). After completing these virtual measures, the study coordinator will lead client participants through a feedback survey and individual feedback interview regarding the Horyzons platform, their online therapist, the PSS, and the community newsfeed. Client participants will be welcomed to share their opinions regarding their experience, including suggestions for how to improve Horyzons in the future.

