The Psychological Wellbeing Scale (Short Form) - Purpose in Life subscale is a 3 item scale. Answers are on a 6 point scale with options "strongly disagree", "moderately disagree", "slightly disagree", "slightly agree", "moderately agree", and "strongly agree". Possible scores range from 3 to 18. Higher scores reflect higher feelings of purpose in life. The Psychological Wellbeing Scale - Purpose in Life subscale is administered in both cohort 1 (Baseline, Mid-treatment, Post-treatment, up to 3 months) and cohort 2 (Baseline, Mid-treatment, Post-treatment, up to 6 months).

10. Qualitative Summaries of Participant Experience in Post-Treatment Feedback (Both Cohorts) [Time Frame: up to 6 months]

This qualitative data will be collected post-treatment from clients and clinicians. Focus groups and individual interviews will discuss usage of the platform and any feedback participants may have. Feedback from participants will be summarized to include common themes regarding likes and dislikes of the platform, implementation within the clinical setting, and participant ideas for future directions. Feedback is elicited at post-treatment in both cohort 1 (Month 3) and cohort 2 (Month 6).

11. Quantitative Summaries of Participant Experience in Post-Treatment Feedback (Both Cohorts)  
[Time Frame: up to 6 months]

This quantitative data will be collected post-treatment from clients and clinicians. Feedback forms will prompt participants to answer questions regarding their experience with the platform on a scale of 1 to 5, with higher scores reflecting a more positive experience. Frequency counts will be included here. Feedback is elicited at post-treatment in both cohort 1 (Month 3) and cohort 2 (Month 6).

12. Mean Change in Questionnaire about the Process of Recovery - Total Score (Cohort 2 Only) [Time Frame: up to 6 months]

The Questionnaire about the Process of Recovery (QPR) - Total Score is a 15-item scale. Answers are rated on a 5-point scale with options "disagree strongly", "disagree", "neither agree nor disagree", "agree", and "agree strongly". Possible scores range from 0 to 60. Higher scores are indicative of recovery. The QPR is administered in only cohort 2 (Baseline, Mid-treatment, Post-treatment, up to 6 months).

13. Mean Change in Modified Colorado Symptom Index - Total Score (Cohort 2 Only) [Time Frame: up to 6 months]

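### The primary mean changes are planned without a confidence interval, and with no use of the mid-treatment scores of clients who have no post-treatment score

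*Combined protocol and SAP*

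**What the plan says.** **Analysis.** The Statistical and Analytic Plan row of the Synopsis describes the analysis as mainly descriptive and lists three summaries for the primary and secondary outcomes: mean, SD and effect size. Section 5.1 names the two primary outcomes as mean changes and lists baseline, mid- and post-treatment administrations in both cohorts. Neither place gives an interval, an analysis set, a rule for missing scores or the SD that standardises the effect size. Section 3.1 states that there are no specific hypotheses. Section 5.4 gives no power basis and says the study will inform later, well-powered trials.

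**Who is assessed, and when.** Section 2.1 (Treatment period) says "Participants in both cohorts will complete study assessments at baseline, mid-treatment, and post-treatment". Section 4.2.2 says "Client participants will complete virtual copies of the UCLA Loneliness Scale, MOS Social Support Survey, SIAS, short form PWS" at post-treatment, with no condition on use of the site. One sentence in Section 2.1 has the client meet staff "for a post-treatment assessment after clients have engaged with the platform for 12 weeks in the first cohort and 26 weeks in the second" cohort. The next paragraph is by calendar: "In the first cohort at baseline, mid-treatment (6-8 weeks), and post-treatment (12 weeks), participants will complete measures of loneliness". The Synopsis (Study Duration) says of cohort 1 that "participation will last 3 months from baseline to post-treatment", and access itself runs "from their date of enrollment up to 3 months in the first cohort".

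**Clients who stop using the site.** Sections 2.1 and 6.1 set out contact attempts after two and four weeks of inactivity. Section 6.1 (Online safety) also allows an account idle for one month to be deactivated after a call, and removes from the system users who break the safe-use guidelines. It says nothing about outcome assessment for either group.

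**The concern.** Change in the psychological measures is the objective marked primary in the Synopsis and in Section 3. The protocol expects some clients to go idle, so some post-treatment scores may be missing. A mean change from baseline to post-treatment then naturally rests on clients who have both scores. If those clients differ in outcome from the ones who leave, the mean describes continuing users only. The direction is not obvious, because a client may stop through lack of benefit or because of improvement.

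At these cohort sizes a bare effect size also hides how little it pins down. That matters for a study meant to inform later trials. The mid-treatment scores, which carry information on clients who leave late, are already being collected, and the plan does not say how they will be used.

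**Working it through.** The plan has no sample-size or precision figure to reproduce. The primary scale ranges do reproduce: 20 items scored 1 to 4 give 20 to 80, and 19 items scored 1 to 5 give 19 to 95, as Section 5.1 states.

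**Inputs from the documents.** The Synopsis gives 25 clients in cohort 1 and 37 in cohort 2. Section 2.2 gives maxima of 30 and 60. Both primary scales are taken at three visits (Section 5.1).

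**Assumed inputs (not in the documents).** Observed effect size 0.30, 20% missing at post-treatment, and correlation 0.6 between visits.

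**Step 1: precision of the effect size.** Let d be the mean change divided by the SD of change, and t = d√n. The 95% limits are the noncentrality values λ for which t lies at the upper and lower 2.5% points of a noncentral t on n - 1 degrees of freedom, divided by √n. For n = 25, t = 0.30 × 5 = 1.50. For n = 37, t = 0.30 × 6.083 = 1.825.

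| Clients analysed | 95% CI for d = 0.30 | Half-width for mean change, t(0.975, n - 1)/√n, in SDs of change |
|---|---|---|
| 25 (cohort 1) | -0.104 to 0.698 | 0.413 |
| 37 (cohort 2) | -0.032 to 0.628 | 0.333 |
| 30 (maximum, cohort 1) | -0.068 to 0.664 | 0.373 |
| 60 (maximum, cohort 2) | 0.040 to 0.558 | 0.258 |
| 20 (25 less 20%) | -0.152 to 0.745 | 0.468 |
| 30 (37 less 20%, rounded) | -0.068 to 0.664 | 0.373 |

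**Step 2: what the mid-treatment scores add.** The simulation used 20,000 trials per setting. Scores at the three visits were trivariate normal with SD 1 and correlation 0.6. True loneliness change was -0.15 at mid- and -0.30 at post-treatment, in baseline SDs. Dropout before post-treatment was logistic in the mid-treatment change, with slope +1 or -1 per SD, set to 20% missing. The likelihood estimate came from regressing the post-treatment score on the baseline and mid-treatment scores.

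| Who leaves | n | Completer mean (SE) | Likelihood estimate (SE) |
|---|---|---|---|
| Poorer responders | 25 | -0.377 (0.198) | -0.300 (0.200) |
| Poorer responders | 37 | -0.376 (0.162) | -0.299 (0.162) |
| Better responders | 25 to 60 | -0.221 to -0.223 | -0.298 to -0.300 |

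The completer mean is therefore off by about 0.38 - 0.30 = 0.08 or 0.30 - 0.22 = 0.08 baseline SD. The likelihood estimate removes this at almost no cost in SE. With 40% missing, the completer means are -0.45 and -0.15, and the likelihood estimate stays at -0.30. With dropout unrelated to change, both give -0.30.

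**Step 3: where the remedy fails** (20% missing, 8,000 trials, n = 25 and 37). If dropout depends on the unseen post-treatment change, the completer mean is -0.46 and the likelihood estimate -0.41. If those who leave also miss mid-treatment, the figures are -0.38 and -0.35. Most of the bias remains in both cases.

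**Units.** Step 1 uses the SD of change and Step 2 the baseline SD. At correlation 0.6 the SD of change is √(2 × 0.4) = 0.894 baseline SD, so 0.30 baseline SD is 0.30/0.894 = 0.34 SD of change. The plan does not say which SD it will use.

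**The case against.** The study is declared exploratory and descriptive, with no hypotheses and no power basis, so neither a test nor a sample size can be demanded. A reader given d and n can rebuild the interval. No bias is shown, since every attrition input above is assumed. Even in the favourable case the gain is small: total error (bias and SE combined) at n = 25 falls from √(0.077² + 0.198²) = 0.21 to 0.20, and at n = 37 from √(0.076² + 0.162²) = 0.18 to 0.16. An account can also be deactivated after one idle month, before mid-treatment at 6-8 or 12 weeks. Such clients may miss both later visits, and there the model helps little.

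Most of this stands, and it limits the point to a cheap improvement. It does not remove it. An interval is itself descriptive, and it can be rebuilt only if the reader knows which SD was used and how many clients were analysed, neither of which the plan promises to report.

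A reader might go further and infer from *engaged* in Section 2.1 that the post-treatment visit depends on use of the site, or that deactivated or excluded clients are dropped from assessment. The documents do not support either reading. The next paragraph of Section 2.1, the Synopsis and Section 5.3 (items 10 and 11) all time the visit by calendar, and weekly engagement is left to the client, so accumulated engagement would have no definition. Assessments are by videoconference with study staff, not through the site. Section 6.1 removes people from the site, not from the study. What remains is one loose phrase and silence on these clients.

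**Conclusion.** The point holds as an inexpensive improvement to the analysis. The primary mean changes have no stated interval, no rule for missing scores and no stated use of the mid-treatment data. With an effect size of 0.30, the 95% CI includes zero at 25 and at 37 clients. Of the four cohort sizes in the documents, only the cohort 2 maximum of 60 excludes it, and narrowly.

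The size and direction of any attrition bias cannot be known from the documents. The figure of about 0.08 baseline SD rests on 20% missing, correlation 0.6 and dropout driven by mid-treatment change. It could run either way, so nothing here shows that the planned summary would flatter Horyzons. The wording in Section 2.1 and the silence on deactivated or excluded clients call for clarification only.

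**What to change.** **Analysis (Synopsis and Section 5).** Beside the completer summary, and for each cohort separately, report a likelihood-based repeated-measures estimate of mean change from the baseline, mid- and post-treatment scores, with visit as a factor. Give 95% CIs for the mean change and the effect size, name the SD used, and report the number assessed at each visit. State that the estimate corrects only for dropout that depends on observed scores and does little for clients who also miss mid-treatment. No hypothesis test is needed.

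**Wording (Section 2.1).** Reconcile the *engaged* phrase with the calendar timing used elsewhere. Confirm that clients whose accounts are deactivated, or who are excluded from the site, are still invited to the post-treatment assessment unless they have withdrawn consent, as Sections 2.1 and 4.2.2 already imply. The deactivation and exclusion rules themselves are not at issue.

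**Cost.** One sentence in Section 2.1 and two or three in Section 5, with no new instrument or visit. The analysis part can be applied to data already collected. The downsides are a little more analysis, some effort to reach idle clients, and a reported effect that may be less favourable.
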